 - C. Non-arrhythmic myocarditis subrgoups (i.e.: fulminant, acute coronary syndrome-like, pericarditis-like, heart failure, nonischaemic dilated /hypokynetic cardiomyopathies of unknown aetiology...).
 - D. Infectious vs. aoutoimmune vs. toxic myocarditis.
 - E. Myocarditis treated by aetiology-based treatment vs. isolated cardiac medical treatment.
 - F. Myocarditis at different disease stages: acute, hyperacute, fulminant, chronic active, post-inflammatory, or active vs. previous vs. non-myocarditis.
 - G. Myocarditis presenting as organ-specific diseases vs. in the context of a genetic disorder or systemic disease.
 - H. Myocardits vs. peri-myocarditis/myo-pericarditis.
 - I. Other analyses.

STUDY DESIGN

Our study, previously designed as a single-center experience, is multicenter, observational and both retrospective and prospective.

Retrospective phase includes all clinical data occurring before the index event (hospitalization or clinically suspected myocarditis) and myocarditis diagnosis. Prospective phase includes all data following index event and myocarditis diagnosis.

Any adult patient with clinically suspected myocarditis, of any clinical presentation and any degree of severity, will be considered as suitable for study enrollment.

Patients will undergo diagnostic and therapeutical strategies considered as clinically indicated in a patient-tailored manner, as suggested by international guidelines recommendations and best local clinical practice. Patients will be free of either accepting or refusing any diagnostic or therapeutical proposal. Whenever accepted, data will be simply collected and analyzed.

Based on clinical presentation, patients will be divided into two groups, arrhthmic (group A) and non-arrhythmic (group NA, including any other clinical presentation).

Independently of A/NA groups, all patients will undergo optimal diagnostic and therapeutic strategies, as summarized in panel A. In parallel, special diagnostic and therapeutical strategies will be performed in patients with arrhythmic presentation or evidence of arrhythmias, as shown in panel B. Proposed flowcharts (panels A and B) represent only an approximate algorithm. Exceptions can be made in single cases, based on clinical indications.

Panel A – Diagnostic and therapeutical workup in all patients.

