After electrical stabilization and support treatment (panel A), including the use of temporary pacemaker as a bridge-to-decision, patients will undergo watchful waiting strategy or definitive device implant. Instead of a pacemaker (PM), ICD will be considered in the presence of high-risk criteria for ventricular tachyarrhythmias, including: a) overlap with Group 1 presentation; b) overlap with Group 2 presentation, especially in the presence of positive EPS; c) other indications for primary prevention ICD implant (severe systolic dysfunction); d) signs of increased tachyarrhythmic risk (scar signs); e) patients with special aetiologies leading to an increased tachyarrhytmic risk (es: cardiac sarcoid, giant cell myocarditis, Chagas disease, overlapping genetic syndromes). In addition, all Group 3 patients will undergo COMT and aetiology-dependent treatment whenever applicable (panel A). A CRT-D or a CRT-P will replace ICD or PM, respectively, whenever indicated.

4. Group 4: supraventricular arrhythmias (atrial fibrillation = AF; atrial flutter = AFlu; atrial tachycardia = AT).

Following acute-phase rate control (RaC), stable rhythm control (RyC) strategy will be considered as the therapeutical target, together with appropriate anticoagulation, as needed. Normal sinus rhythm will be obtained through either electrical or pharmacological cardioversion. In patients with unsuccessful attempts of sinus rhythm conversion, optimal treatment of active myocarditis will be considered as a primary target. Following myocarditis healing, in the presence of persistent arrhythmias, patients will be considered for RyC via electrical or pharmacological cardioversion. Transcatheter ablation will be an option for patients with drug-symptomatic, recurrent or refractory arrhythmias. Permanent RaC strategy will be considered only in non responders. Widespread use of implantable loop recorders will apply, as clinically indicated. In addition, all Group 4 patients will undergo COMT and aetiology-dependent treatment whenever applicable (panel A).

STUDY POPULATION

We will enroll adult patients (age \geq 18 y), of any gender or ethnic group, evaulated for clinically suspected myocarditis. Patients can be enrolled from any medical environment or department, including inpatients, outpatients, and patients transferred from other hospitals. The same inclusion criteria will apply to the multicenter study (see below).

INCLUSION CRITERIA

- Written informed consent.

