- Age \geq 18 years.

- Clinically suspected myocarditis [1].
- Enrollment performed by one of the participating Centers.

EXCLUSION CRITERIA

- Absence of written informed consent.
- Age < 18 years (paediatric population).

VARIABLES AND ENDPOINTS

The main study variables are reported in Table 1 and in CRF. Endpoints will include:

- Major endpoints: death; cardiac death; malignant ventricular arrhythmias (= VT, VF, appropriate ICD therapy); heart transplantation; end-stage heart failure.
- Minor endpoints: minor arrhythmias (NSVT; supraventricular arrhythmias; bradyarrhythmias); structural or functional myocardial abnormalities (any chamber dilation, systolic or diastolic dysfunction, including strain analysis, pericardial, vascular or valvular involvement, any other detectable abnormalities); abnormalities detectable by advanced imaging techniques (Lake Louise criteria and T-mapping techniques at CMR; any qualitative or quantitative imaging abnormality detectable by CMR, DECT or PET scan, or other imaging techniques, alone or in association); clinical variables (signs and symptoms related to cardiac or multisystemic disease; identification of associated diseases); blood exams abnormalities (inflammatory indexes; cardiac injury, inflammation or stress biomarkers; cardiac and extracardiac autoantibodies; genetic tests; tissue/organ damage indexes; markers of treatment toxicity; others); anatomical or functional abnormalities of coronary macro or microvascular structures (coronary angiography; CT scan; histology; provocative stress tests, nuclear medicine techniques); necessity of invasive elctrophysiological techniques (electrophysiological study; arrhythmia ablation; device implant) and related findings; indications and timing for primary and secondary prevention device implant, in relation with different therapeutic strategies; myocarditis recurrences; response to general and specific treatement; multiparametric modeling of prognostic risk stratification and response to treatment prediction; elaboration of multidisciplinary workup models.

The main pimary and secondary variables are reported in detail in Table 1.

Tabella 1

N	Aim	N patients	Primary Variables	Secondary variables

MYOCAR - Version V03 - Multicenter

Principal Investigators: [name] - [name]

1 Comparison between EMB 1000 Diagnostic Inflammation 	ory activity (presence; type;
and second level imaging concordance quantificat	
findings • Fibrosis (p	resence; type; quantification)

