 F. Different myocarditis stages and differential diagnoses G. Isolated vs. in the context o a systemic disease or genetic disease H. Myocarditis vs. perimyocardis/ myopericarditis 	 Validation of biomarkers and imaging techniques in monitoring response to treatment (group E) Identification of optimal follow-up timeline Other analyses
-------------------------------------------------------------------------------------------------------------------------------------------------------------------------------------------------------------------------------------------------------	-------------------------------------------------------------------------------------------------------------------------------------------------------------------------------------------------

FOLLOW-UP VARIABLES

Any quantitative and qualitative parameters detectable by medical history, objetcive examination, biomarkers, 12-leads ECG, signal averaged ECG, continuous telemonitoring (during nwe hospitalization or in device carriers), Holter ECG (at least 24-hours, possibly 12-leads), color Doppler transthoracic echocardiogram, coronary angiography or CT scan, stress tests, CMR, DECT, PET scan (alone or in association/fusion), genetic tests, tilting test, electrophysiological study (either invasive or nonivasive), electroanatomical map, any other imaging or laboratory exam identified as clinically-relevant.

FOLLOW-UP TIMELINE

A clinical time zero (t0) will be considered as the start point for FU. t0 indicates the timing of myocarditis diagnosis, as assessed by EMB (first choice) or by imaging techniques (secondo choice).

FU calendar will be variable based on clinical indications. As a general line, intensive FU will be planned for the first two years (month 3, month 6, month 9, month 12, month 18, month 24). For patients needing a strict control for relevant clinical issues, minimal FU reassessment is set at 2 weeks timespan. In the absence of clinical issues, from month 24 FU will be performed every 6-12 months up to the end of the study.

FOLLOW-UP EXAMS

- Standard FU: cardiological (or multidiciplinary) assessment 1-2/y with blood exams (at least troponin, natriuretic peptides, and inflammatory indexes), 12-leads ECG, Holter ECG monitoring, device interrogation (in device carriers), and color Doppler transthoracic echocardiogram. Second-level imaging techniques (CMR, DECT, PET scan) or other exams will be performed based on clinical indications.

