- Intensive FU: cardiological (or multidiciplinary) assessment 1-2/y with blood exams (at least troponin, natriuretic peptides, and inflammatory indexes), 12-leads ECG, Holter

ECG monitoring, device interrogation (in device carriers), and color Doppler transthoracic echocardiogram. Minimal reassessment timespan is 2 weeks. At least one second-level imaging techniques (CMR, DECT, PET scan) will be performed by 12 months (approximately at 3, 6, 9, or 12 months based on clinical indications). Exercise stress test will be performed whenever clinically indicated, usually not before proved myocarditis healing. Other exams will be performed based on clinical indications.

STUDY DURATION

Estimated study duration is 23 years (from Jaunary 2013 to December 2035). In detail:

- Retrospective enrollment: from January 2013 to local institute review board approval.
- Prospective enrollment: from local institute review board approval to Dicember 2025 (estimated enrollment end).
- FU duration per patient: 10 years.
- Estimated last FU for last enrolled patient: December 2035.

CONFOUNDING FACTORS

Not applicable.

EPIDEMIOLOGIC DATA

Because of multiple clinical presentations and heterogeneous diagnostic techniques, myocarditis incidence is widely variable [1].

At our institution, the mean rate of clinically suspected myocarditis is not inferior to 4 new cases/month. Epidemiology may be different at other centers.

Target numbers reported in Table 1 are reasonable.

DATA COLLECTION AND STATISTICAL ANALYSIS

Two enrollment modalities are accepted for this study: 1) prospective enrollment: at myocarditis diagnosis (following local institute review board approval); 2) retrospective enrollment: during FU of myocarditis patients (diagnosed before local institute review board approval).

Considering incidence rate, local and general epidemiology, enrollment of 1000 myocarditis cases by December 20205 is expected, including retrospective and prospective enrollment. For aim 1, 95% confidence intervals of 81-89% and of 75-85% are estimated for EMB and CMR, with 85% and 80% sensitivity, respectively. These data are consistent with updated knowledge. EMB will be considered as the diagnostic gold standard, as indicated [1].

Both baseline and FU data will be collected for each enrolled patient. CRF form reports the main study variables, in the form of an Excel document.

Statistical analyses will be performed by certified programs (i.e. SPSS).

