Data will be presented as mean/median and standard deviation/interquartile range, or as contingency tables, depending on variables type and distribution. Parametric and non-parametric tests will be used accordingly. Confidence intervals will be set at 95%. Statistical significance threshold will be set at p < 0.05. Regression models will be used for univariable and multivariable risk stratification and survival analyses.

Either in all patients or in subgroups, appropriate statistical tests will be used for general and specific analyses, as needed to address each study aim (Table 1).

ETHICAL ISSUES

Our study will be performed in accordance with Helsinki Declaration and current laws regarding observational prospective and retrospective studies.

Diagnostic and therapeutical workup will not differ from daily clinical practice a tour hospital, as the result of updated international scientific evidence, integrated by the experience of a referral center for myocarditis and arrhythmias management, aiming at the best patients' interest. Follow-up timeline and diagnostic exams will be required as clinically needed. No randomization procedures will be performed. Patient grouping will be "spontaneous", based on clinical features and personalized overall workup. This study will respect the autonomy principle for any patient. At any time, patients will be free to accept or refuse any diagnostic or therapeutical proposal. As in daily clinical practice, critical or exceptional diagnostic and therapeutical options will be discussed in a multisiciplinary team and shared with patients, as needed. Per protocol, data will be simply collected and analyzed, without interfering with the best clinical practice. Thus, for any diagnostic exam or treatment, no special adverse reactions are expected, as compared to what observed in daily clinical practice.

Written informed consent will be obtained for any enrolled patient. No physical or psychosocial risks are expected regarding study procedures, informed consent, or authorization to use personal data.

Institutional review board evaluation is necessary to approve the present study protocol.

All data will be made anonymous. Analyses results will be published in international medical journals with impact factors.

REFERENCES

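### Retrospectively enrolled patients must survive to give consent, yet their follow-up counts from diagnosis, so mortality is understated unless they enter the risk set at consent

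*Protocol*

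**What the plan says.** Study Design states: "Our study, previously designed as a single-center experience, is multicenter, observational and both retrospective and prospective". Data Collection and Statistical Analysis accepts two routes of entry. Prospective patients enter at diagnosis, after the local board has approved the study. The other route is "retrospective enrollment: during FU of myocarditis patients (diagnosed before local institute review board approval"). Under Study Duration the retrospective window opens in January 2013 and closes at each centre's own board approval. Both routes count toward the expected 1000 cases, and no analysis by route is described.

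Consent applies to both routes. It is an inclusion criterion ("Written informed consent"), its lack is an exclusion criterion ("Absence of written informed consent"), and Ethical Issues repeats that "Written informed consent will be obtained for any enrolled patient". No waiver or records-only route is given for a patient who died before being asked.

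Follow-up Timeline sets one origin for all: "t0 indicates the timing of myocarditis diagnosis, as assessed by EMB (first choice) or by imaging techniques (secondo choice"). Study Design adds: "Prospective phase includes all data following index event and myocarditis diagnosis". Death and cardiac death are among the five major endpoints, differences in major outcomes are the primary variable of aim 5 in Table 1, and regression models for survival are planned. Confounding is declared not applicable.

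**The concern.** Taken together, these rules produce left truncation, or immortal time. A patient diagnosed in 2014 and enrolled in 2020 is in the study only because he or she lived to 2020. Someone diagnosed on the same day who died in 2015 cannot be enrolled. If the survivor is counted at risk from 2014, the denominator contains years in which no death could be observed.

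The phase definition makes this easier to miss. All data after diagnosis are called prospective, so an analyst who restricts to the prospective phase keeps the immortal time. The split that matters is by enrolment route.

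Mortality estimates and prognostic models would lean toward good outcome. Comparisons under aims 3 and 5 could also be distorted where groups differ in retrospective share or early lethality. Such a difference is plausible here: the retrospective window ends on a different date at each centre, and the head centre is an arrhythmia referral centre, so case mix and retrospective share may vary together. The documents do not allow the size or direction of that distortion to be stated. Non-fatal events before consent can be recorded in survivors and are affected only indirectly.

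**Working it through.** The protocol has no mortality figure to reproduce, so the check shows direction and a plausible range.

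**Inputs from the protocol.** Retrospective window from January 2013; version date 20 February 2020, 85.7 months later; enrolment to December 2025, 156 months in all; at least 4 suspected cases a month at the head centre; 1000 cases in total.

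**Assumptions.** Mortality 10% in year 1, then 2% a year: S(t) = 0.9^t up to 1 year, then 0.9 × 0.98^(t−1). Diagnoses uniform over the window, consent at approval, all survivors consent. The retrospective share of incident cases is either 4 × months/1000 (head centre only) or months/156 (constant accrual).

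**Formula.** With lag A uniform on (0, L), retrospective survival counted naively from t0 is E[S(max(t, A))] / E[S(A)]. It is pooled with S(t) for prospective patients, the retrospective share being weighted by E[S(A)].

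**Worked case, approval February 2020 (L = 85.7/12 = 7.14 years).**

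1. ∫S over 0–1 = 0.1/0.1054 = 0.949. ∫S over 1–7.14 = 0.9 × (1 − 0.98^6.14)/0.0202 = 5.198. E[S(A)] = 6.147/7.14 = 0.861.
2. At 1 year the numerator is (1 × 0.900 + 5.198)/7.14 = 0.854. Naive retrospective mortality is 1 − 0.8539/0.8608 = 0.80%, against a true 10%.
3. Share 4 × 85.7/1000 = 0.343: weights 0.343 × 0.861 = 0.295 and 0.657. Pooled: (0.295 × 0.80 + 0.657 × 10)/0.952 = 7.15%.
4. Share 85.7/156 = 0.549: weights 0.473 and 0.451. Pooled: (0.473 × 0.80 + 0.451 × 10)/0.924 = 5.29%.

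**All base cases** (truth 10.00% at 1 year, 16.99% at 5 years):

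| Approval assumed | L (years) | Share | E[S(A)] | Naive 1-year | Naive 5-year |
|---|---|---|---|---|---|
| February 2020 | 7.14 | 34.3% / 54.9% | 0.861 | 7.15% / 5.29% | 13.02% / 10.43% |
| January 2017 | 4 | 19.2% / 30.8% | 0.892 | 8.49% / 7.55% | 15.23% / 14.14% |
| January 2015 | 2 | 9.6% / 15.4% | 0.920 | 9.35% / 8.95% | 16.34% / 15.95% |

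**Variants at 1 year.**

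- True mortality 5%: 3.5–2.6% (2020) or 4.7–4.5% (2015).
- True mortality 20%: 14.8–11.1% (2020) or 18.8–18.1% (2015).
- Consent at a visit up to 12 months after approval: 7.0–5.1%, 8.4–7.3% and 9.2–8.7% for the three dates. This is an assumption, suggested by the visit rule: "In the absence of clinical issues, from month 24 FU will be performed every 6-12 months up to the end of the study".

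**Does delayed entry repair it?** In simulations of 1,000,000 incident cases per scenario, Kaplan-Meier with entry at consent gave 9.96–10.04% at 1 year and 16.93–17.02% at 5 years. A separate simulation used another hazard shape: 5% dying in the first 3 months, then 0.02 a year, 55% retrospective. True mortality was 6.4% and 13.6%; counting from t0 gave 3.2% and 8.3%; delayed entry gave 6.4% and 13.5%.

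**Other endpoints.** For a composite of death and a non-fatal event (assumed 15% first-year non-fatal risk, unrelated to death; truth 23.5% at 1 year), the naive figure is 21.1–19.5% (2020) or 22.9–22.6% (2015), and delayed entry gives 23.5–23.6%. The non-fatal event alone hardly moves: truth 14.2–14.4%, recorded 13.5–14.7%.

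**The case against.** The strongest reply is that t0 at diagnosis is a proper time scale, that the protocol neither prescribes nor excludes delayed entry, and that such detail belongs in a SAP, which may exist. This makes the concern conditional but does not remove it. The enrolment rule, the consent rule, the origin and the pooled total are all fixed in the protocol, and together they create the bias. A SAP that specifies delayed entry would resolve the point, provided that consent dates are collected.

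A second reply is that the size is wholly assumed and its range is not a bound. That is right. If head-centre patients consented at diagnosis under the former single-centre design, they carry no lag; centres approved after February 2020 would have a longer one. The lower share divides suspected cases at one centre by a multicentre enrolment target. Incomplete consent also matters. With 20% high-risk patients (hazard ratio 3), a 34% share and a 7.1-year window, the naive 1-year figure moves from 7.2% to 8.1% if half of the low-risk survivors consent, and to 8.8% if a quarter do. The direction at 1 year stayed the same; the size did not.

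Three smaller points stand. The five major endpoints are not ranked and no mortality estimate is sized. Prognostic work under aims 2 and 4 is touched wherever death is the outcome. Delayed entry for composites discards events recorded before consent.

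**Conclusion.** The concern holds and should be fixed. Under the protocol's rules, ordinary survival analysis from t0 understates death, cardiac death and composites that include death, unless retrospective patients enter the risk set at consent. In the base case the shortfall at 1 year runs from about half a point (approval 2015, lower share) to nearly 5 points (approval February 2020, higher share), against a true 10%. These sizes rest on assumed mortality, approval dates, shares and consent behaviour. The direction was the same in every scenario examined at 1 year. Nothing can be said about the size or direction of distortion in subgroup comparisons. The diagnostic comparison in aim 1 is not affected by this argument.

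**What to change.** 1. Record each patient's consent date and enrolment route. Define the route by the two enrolment modalities in Data Collection and Statistical Analysis, not by the phases in Study Design.
2. For death, cardiac death and composites that include death, keep t0 as the time scale with delayed entry at consent (left-truncated Kaplan-Meier and Cox). A patient whose composite event came before consent does not enter that risk set.
3. Ask the ethics boards whether eligible patients who died before consent may be included from records. Where this is granted and capture is complete, that centre's patients can enter at t0. Elsewhere, log the number of such deaths.
4. Report prospectively enrolled patients alone as a sensitivity analysis, because delayed entry assumes that entry time is unrelated to prognosis. Note that unstable patients who die before consent may be missed there too.
5. For non-fatal endpoints, keep pre-consent data, report by route, and state that the retrospective part is conditional on survival to consent.

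The administrative cost is protocol or SAP wording, two fields per patient and, for step 3, an ethics query. The statistical cost is fewer patients at risk early. With 1000 enrolled, the 95% half-width for 1-year mortality rises from 1.6 to 2.2 points (34% share, 7.1 years), from 1.4 to 2.6 (55%, 7.1 years), or from 1.8 to 1.9–2.0 (10–15%, 2 years). The narrower intervals surround a biased estimate. For composites, the pre-consent events set aside come to about 2–22% of events under assumed rates. These can still be described by route under step 5.

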- 3. Arrhythmic myocarditis is largely underdiagnosed and uninvestigated. Importantly, myocarditis presenting with arrhythmias requires specific diagnostic, prognostic and therapeutic considerations [2]. At our hospital, which is an international referral center for ventricular arrhythmias management and ablation, a relevant number of patients with unexplained arrhythmias had myocarditis as underlying aetiology. Our experience may considerably improve knowledge and management of arrhythmic myocarditis.
- 4. The role of CMR, as well as alternative nonivasive imaging techniques, in defining myocarditis healing is a relevant issue. In particular, optimal timing for follow-up diagnostic reassessment is still to be defined, in patients with myocarditis at different inflammatory stages, either with or without aetiology-dependent treatment [4,7].
- 5. Uniformly-designed studies are lacking, to compare myocarditis among different patient subgroups, differing by variables like: clinical presentations, myocarditis stage, associated cardiac or extra-cardiac diseases, aetiology-based treatment, associated arrhythmic manifestations, diagnostic workup, and devices or ablation treatment [8,9,10].

AIMS

Our study has multiple aims (full detail in Table 1).

- 1. To compare EMB with nonivasive diagnostic techniques (CMR, DECT, PET scan, either alone or in association).
- 2. To assess the role of blood biomarkers for identification of aetiology, predisposition, prognosis, response to treatment, inflammatory activity, clinical presentation.
- 3. To describe myocarditis presenting with arrhythmias, with special focus on ventricular arrhythmias at different myocarditis stages and in different clinical contexts. To validate and generalize our model for optimal diagnostic and therapeutical management of arrhythmias in myocarditis patients (given the role of our hospital as an international referral center for arrhythmias ablation and management).

- 4. To evaluate the timing needed for myocarditis healing in different patients subgroups, as assessed by nonivasive imaging techniques (CMR, DECT, PET scan), either alone or in association.
- 5. To compare patients subgroups of myocarditis, in terms of epidemiology, aetiology, prognosis, and diagnostic-therapeutical strategies. Among the others, the main study subgroups will be:
 - A. Arrhythmic vs. non-arrhythmic myocarditis.
 - B. Arrhythmic myocarditis subgroups.

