	arrhythmias during FU)				• • •	Identification of optimal timing for any electrophysiological/arrhythmologic procedure Role of pharmacological antiarrhythmic treatment Role of aetiology-specific treatment on arrhythmic outcomes Identification of criteria for device implants (PM, ICD, S-ICD, CRT-D) in myocarditis patients Validation of therapeutic strategies and their optimal timing in patients with supraventricular arrhythmias, bradyarrhythmias, or ventricular arrhythmias Correlation between arrhytmia type/features with any other diagnostic exam performed at baseline or during FU (mainly EMB, CMR/DECT/PET, echocardiogram, stress tests,
					•	blood exams, genetic/blood/tissue/cell biomarkers) Indications and timing for device (ICD, CRT-D) implant in primary prevention, based on multiparametric risk assessment, and in relation to different general and aetiology- dependent treatments Other analyses
4	Evaluation of healing timing in myocarditis	500	•	Any degree of recovery by 3, 6, 9, 12 and > 12 months	• • • • •	Comparison of healing times in treated vs. untreated patients Correlations between healing times and clinical presentation types Correlations between healing times and any biomarker Correlations between healing times and any outcomes Validation of exercise stress test role after myocarditis healing Evaluation of PET scan or other diagnostic techniques as alternatives to CMR in special populations Other analyses
5	 Subrgoup analyses A. A vs. NA groups B. A myocarditis subgroups C. NA myocarditis subgroups (including fulminant) D. Infective vs. autoimmune vs. toxic forms E. Tretaed by aetiology- driven therapy vs. standard cardiological treatment 	500 (hugely variable in each subanalys is)	•	Differences in major outcomes	• • • • • •	Differences in minor outcomes Differences in any biomarker Differences in any diagnostic exam Differences in aetiology Differences in predisposition Differences in predisposition Differences in inflammatory activity Differences in pericardial involvement Differences in systemic involvement Differences in systemic involvement Differences in arrhythmias types and features Differences in clinical presentation Differences in treatment response, including novel treatments Validation of local aetiology/pathophysiology- dependent treatments (group E)

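### One p < 0.05 threshold covers about 40 aim 5 comparisons and an open-ended biomarker search, and nothing is labelled exploratory

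*Protocol*

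**What the plan says.** The threshold appears once, in the protocol's section Data collection and statistical analysis: "Statistical significance threshold will be set at p < 0.05". Confidence intervals are set at 95% in the same paragraph. The next paragraph gives the scope: "Either in all patients or in subgroups, appropriate statistical tests will be used for general and specific analyses, as needed to address each study aim".

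The material to which this applies is set out elsewhere in the protocol:

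- **Endpoints** (Variables and endpoints): "Major endpoints: death; cardiac death; malignant ventricular arrhythmias (= VT, VF, appropriate ICD therapy); heart transplantation; end-stage heart failure". The five are listed side by side. No composite is defined and none is put first.
- **Contrasts** (Aims, aim 5): eight lettered items, A to H, followed by "I. Other analyses".
- **Aim 5 in Table 1**: the primary variable is "Differences in major outcomes". The secondary column has 11 distinct lines of differences, some of them whole classes, such as "Differences in any biomarker".
- **Aim 2 in Table 1**: a search across cell, tissue, genetic and circulating markers, including prognostic markers and markers associated with treatment. No number of markers is given.
- **All five aims in Table 1** close with an open item for further analyses.

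Table 1 does separate primary from secondary variables, but the threshold is the same for both. No result is described as exploratory.

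**The concern.** A threshold of 0.05 limits the error of one test. Here it is the only stated rule for a large, open set of tests, and no endpoint or contrast is marked as the one on which aim 5 will be judged. Applied as stated, any result below 0.05 could be reported as significant, whichever subgroup, endpoint or biomarker produced it.

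This matters because of the conclusions the protocol wants to draw. It aims to validate and generalize a management model for arrhythmias, to validate treatment strategies, and to identify prognostic biomarkers and criteria for device implants. Some aim 5 subgroups will also be small: Table 1 gives 500 patients for the aim and says the number varies greatly between subanalyses. A reader of the publications could not separate a real subgroup or biomarker effect from the number of significant results that chance alone would produce.

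**Working it through.** **Inputs.** Per-test level 0.05 (Data collection and statistical analysis); 5 major endpoints (Variables and endpoints); 8 contrasts, A to H (Aims, aim 5); 11 distinct secondary lines for aim 5 (Table 1, repeated lines counted once). The protocol gives neither the share of true null hypotheses nor the correlation between tests, so both are assumptions below.

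**The plan's own figure.** One test at 0.05 has a 5% false-positive probability. The protocol states no error rate for any set of tests.

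**Aim 5, primary variable.** Taking one overall test per contrast and endpoint, 8 × 5 = 40 tests.

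- Expected false positives if all nulls hold: 40 × 0.05 = 2.0. This does not depend on correlation.
- Chance of at least one, independent tests: 1 − 0.95^40 = 0.871, or 87%.
- Chance of at least one, correlated tests (simulated two-sided z tests):

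| Correlation pattern, 40 tests | At least one false positive |
|---|---|
| 0.3 between endpoints within a contrast | 85% |
| 0.5 between endpoints within a contrast | 80% |
| 0.8 between endpoints within a contrast | 66% |
| 0.6 within a contrast and 0.3 between contrasts | 69% |

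Some correlation is certain, because death includes cardiac death and the contrasts reuse the same patients. If all 40 tests were equally correlated at 0.5 or 0.8, the figures would be 57% and 28%. That is less plausible, because the contrasts divide patients by different features (presentation, aetiology, stage, treatment).

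**Sensitivity to the count.**

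- One composite in place of five endpoints: 8 tests, 8 × 0.05 = 0.4 expected, 1 − 0.95^8 = 34%.
- Without B and C, which name sets of subgroups but no comparison: 6 × 5 = 30 tests, 1.5 expected, 1 − 0.95^30 = 79%.
- Only half of the 40 nulls true: 20 tests, 1.0 expected, 1 − 0.95^20 = 64%.
- Pairwise tests within B, C, D and F, which have more than two groups, would raise the count above 40.

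The three percentages in this list assume independence.

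**Aim 5, secondary variables.** 8 × 11 = 88 cells, but they cannot all be nulls. About ten differ by definition or by construction: arrhythmia type in A and B; clinical presentation in A and C; aetiology in D; inflammatory activity in F; systemic involvement in G; pericardial involvement in H; and aetiology and activity in E, since aetiology-dependent treatment is reserved for active disease of biopsy-proved aetiology. Removing them leaves 78 cells and at most 78 × 0.05 = 3.9 expected false positives at one test per cell. Further true differences would lower this figure, and the lines that cover whole classes would raise it.

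**Aim 2.** For m null biomarkers the expected number of false positives is 0.05 × m. The protocol gives no m. Purely as a range, m = 20, 100 and 200 give 1, 5 and 10.

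**The case against.** The strongest reply is that multiplicity methods and the choice of a lead test are commonly left to a statistical analysis plan, which may exist and is not shown. A nominal 0.05 does not forbid adjusted p-values. The study is observational, no randomised treatment comparison depends on the threshold, aim 1 is planned by precision, and 95% confidence intervals are already specified. All of this stands, and it limits the weight of the point. A reader might infer that the protocol is deficient because it contains no adjustment procedure; the protocol alone does not support that. The point rests on what it does state: one flat threshold for every aim and subgroup, joined to language of validation and identification and with no exploratory label.

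A second reply is that the 40 tests are inferred. This is also fair. The protocol does not say that each endpoint is tested separately, and it does not exclude a composite. The count is the natural reading of the endpoint list and the aim 5 row together, and the working shows how far the figures fall under narrower readings.

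A third reply is that not all nulls can be true. Group A is defined by arrhythmic presentation, and malignant ventricular arrhythmia is a major endpoint, so a real difference there is to be expected. The figure of 2 is therefore what chance would yield if nothing were going on, not a forecast.

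**Conclusion.** The point holds as a cheap improvement. As written, the protocol sets one threshold, with no stated adjustment, for about 40 aim 5 primary comparisons and an open biomarker search, and nothing marks any of them as exploratory. If all 40 nulls held, 2 false positives would be expected, with an 87% chance of at least one under independence and roughly 66-85% under plausible correlation. These figures assume separate testing of the five endpoints, one overall test per contrast, and correlations that the protocol does not give.

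A reader might go further and infer that false-positive findings are practically certain. For the 40 tests that is too strong. For a larger set the probability does rise (64 independent true nulls give 1 − 0.95^64 = 96%), but the documents fix neither the number of true nulls nor the correlations, so no firm figure can be attached. Nor should the study be described as validating device criteria: Table 1 says those are to be identified, while validation is claimed for therapeutic strategies and local treatments.

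**What to change.** Keep the threshold sentence and add two rules to the same section:

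1. For aim 2, control the false discovery rate at 5% by the Benjamini-Hochberg method across all biomarker tests run under that aim, whether Table 1 lists them as primary or secondary variables.
2. Report the aim 5 subgroup comparisons, all other secondary variables and every open-ended analysis as estimates with 95% confidence intervals, labelled exploratory, with no claim of significance based on p < 0.05 alone.

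Rule 1 takes precedence for aim 2 biomarkers, so the two do not conflict where a biomarker is listed as a secondary variable. The primary variables of aims 1, 3 and 4 are not changed by these rules.

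Naming a single lead test for aim 5 is not advised here. The obvious candidate, arrhythmic against non-arrhythmic presentation on a composite that includes malignant ventricular arrhythmia, is close to circular. Because enrolment reaches back to January 2013, a choice made now could also follow sight of the data.

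The cost is a change of wording and fewer results that can be called significant. Enrolment, data collection and patient care are unaffected.
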